9.8 QUALITY CONTROL

Regarding quality control procedures around the data, the Medicare administrative data collection occurred in the past and access to the data is being provided by █████. No additional insight into the data collection procedures is available beyond that which has been published by █████. As a result, we are relying on quality control measures implemented by █████ during data collection.

Regarding quality control procedures around the analyses, the following quality assurance and quality control measures will be applied to all programming that executes data extraction and transformation by █████

- Check program logs for notes, warning messages, and errors
- Check derived data values against source data for a patient sample to ensure correct derivation
- Verify that variables needed to support tables/listings/figures/ are found in the derived data set
- Check that data fields are not truncated
- Check data points for values outside expected ranges, where appropriate

Proprietary confidential information © 2023 Boehringer Ingelheim International GmbH or one or more of its affiliated companies

- Check that data are rounded correctly and in accordance to the analysis plan
- Check that abbreviations, range categories, and subgroups conform to the analysis plan
- Ensure the consistency of sample counts across relevant tables/listings/figures
- Check formats consistent with the analysis plan
- Ensure no typos, misspellings, or false values
- Check that summary statistics are correct; check at least one category in each summary table against the data listings
- Check that data are in accordance with the Data Plan
- Check that subgroups conform to the Data Plan
- Ensure there are no duplicate observations

9.9 LIMITATIONS OF THE RESEARCH METHODS

The study has several limitations, including:

- The data source consists of administrative claims data, which do not include important determinants of health care resource use and cost outcomes that may be correlated with the adherence exposure, such as IPF disease severity.
- Although the outcomes should be measured accurately, the adherence exposure is necessarily based on prescription fill data from claims and may mismeasure actual nintedanib use.
- Sample selection bias may arise from the design decision to exclude patients who do not have at least 12 months of follow-up data after nintedanib initiation for primary outcomes (and 24 months for secondary outcomes).
- Generalizability may be limited to IPF patients who are continuously covered under fee-for-service Medicare, including Parts A, B and D.

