Population:	The study sample will consist of community-dwelling Medicare beneficiaries with IPF who initiate treatment with nintedanib.	
Variables:	
The main exposure will be a five-category measure of adherence trajectory to nintedanib in the year following initiation.
 
Outcomes will reflect inpatient hospitalization (any and number of days) and health care spending for both all-cause and IPF-related care.
 
A range of covariates will be measured during the baseline period and at the index date, including baseline patient demographic characteristics (e.g., age, sex, race/ethnicity), residential location, clinical characteristics (e.g., comorbidity index, IPF-related health care costs and use), and all-cause health care costs and use.
	
Data sources:	This study will use administrative enrollment and claims data from the U.S. federal Medicare program for beneficiaries aged 65 years and older who were continuously enrolled in Original Medicare insurance coverage, including Parts A, B and D. The study will use Medicare data covering the period from October 1, 2013, through December 31, 2020.	
Study size:	Based on our prior study, the sample for analysis of the primary outcomes will consist of 1,798 Medicare beneficiaries with IPF who initiated nintedanib between October 1, 2014, and December 31, 2018. The sample available for the secondary outcomes will be smaller by an unknown amount due to loss to follow-up.	
Data analysis:	
Mean health care cost and use outcomes will be compared between pairs of nintedanib adherence trajectory membership categories using a regression modeling framework. Unadjusted means will be compared first using an “empty” linear regression model specification (with no covariates or weights). Adjusted means will then be compared using a “doubly robust” generalized linear model (GLM) specification.
 
Potential confounding by observed covariates will be addressed in two ways to achieve double robustness. The first way will be to calculate observation-level inverse propensity weights that balance covariates
	

BOEHRINGER INGELHEIM Group of Companies**NIS Protocol****BI Study Number 1199-0520****Page 9 of 35****c42255024-02**

Proprietary confidential information © 2023 Boehringer Ingelheim International GmbH or one or more of its affiliated companies

Name of company: Boehringer Ingelheim			
Name of finished medicinal product: Nintedanib (Ofev)			
Name of active ingredient: Nintedanib (Ofev)			

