9.3.2 Outcomes

The primary outcome will be total all-cause medical costs, which will be calculated as the sum of total amounts paid (by payers and patients) for all medical services. Types of medical services covered by Medicare include inpatient facility, outpatient facility, skilled nursing facility, home health care, hospice, durable medical equipment, and clinician office visits (and other services covered under the Part B benefit). This outcome will exclude spending on outpatient pharmacy (as covered under the Part D benefit).

The secondary outcomes will be:

1. Total IPF-related medical costs, which will be calculated as the sum of total amounts paid (by payers and patients) for all medical services for an IPF-related reason (at least one IPF diagnosis code).
2. All-cause inpatient hospitalization
3. IPF-related inpatient hospitalization.

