9.3.3 Covariates

Study covariates are listed here and will be measured at the index date or during the 12 months prior.

Variable	Description
Demographic and socioeconomic characteristics	
Age	Age as of index date in years rounded to the nearest whole number will be calculated based on the difference between the beneficiary's birth date and index date.
Age group	Age group will be a categorical variable for age defined as one of 65–74, 75–84, 85+.
Female	Female will be a binary indicator for whether the beneficiary was female as indicated on the enrollment record covering the index date.
Race	Race will be a categorical variable for the beneficiary's self-reported race/ethnicity taking the

BOEHRINGER INGELHEIM Group of Companies

NIS Protocol

BI Study Number 1199-0520

Page 18 of 35

c42255024-02

Proprietary confidential information © 2023 Boehringer Ingelheim International GmbH or one or more of its affiliated companies

Variable	Description
	categories Non-Hispanic White, Black or African-American, Other, Asian/Pacific Islander, Hispanic, American Indian/Alaska Native, and unknown race from the enrollment record covering the index date.
Census region	Census region will be a categorical variable defined by categorizing the beneficiary's state of residence into Census regions (Northeast, South, Midwest, West) from the enrollment record covering the index date.
Index year	Index year will be a categorical variable defined as the year of the index date and will take the values, 2014, 2015, 2016, 2017 or 2018.
Social deprivation index	Social deprivation index will be a continuous variable ranging between 0 and 100 representing the Social Deprivation Index for the beneficiary's residential ZIP Code as calculated by the Robert Graham Center. Social Deprivation Index "is a composite measure of seven demographic characteristics collected in the American Community Survey (ACS): percent living in poverty, percent with less than 12 years of education, percent single parent household, percent living in rented housing unit, percent living in overcrowded housing unit, percent of households without a car, and percent non-employed adults under 65 years of age." This version was calculated in 2015 using data from 2015 and updates the original version created by Butler et al. (2013). Higher values for the Social Deprivation Index indicate more social deprivation.
Clinical characteristics	

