Total pharmacy spending	A continuous, non-negative variable representing the total amount paid by all parties for outpatient prescription medications as reported in Part D claims during the baseline period.
OOP pharmacy spending	A continuous, non-negative variable representing the total amount paid out-of-pocket by the beneficiary for outpatient prescription medications

Variable	Description
	as reported in Part D claims during the baseline period.
Inpatient hospitalization use and spending	
Any inpatient stay	A binary indicator for whether a beneficiary had at least one inpatient hospitalization for any cause during the baseline period.
Inpatient stay count	A count of the number of inpatient hospitalizations for any cause a beneficiary had during the baseline period.
Inpatient length of stay	A count of the number of days (length of stay) a beneficiary was hospitalized in an inpatient facility during the baseline period. Length of stay for each inpatient hospitalization claim will be calculated as the arithmetic difference between each claim's from and through dates.
Total inpatient spending	A continuous, non-negative variable representing the total amount paid by all parties for all inpatient hospitalizations (for any cause) as reported in inpatient facility claims during the baseline period. This is calculated as the sum of the Medicare payment amount, the Medicare per diem amount, the non-Medicare payer amount, and the patient OOP amount.
OOP inpatient spending	A continuous, non-negative variable representing the total amount paid out-of-pocket by the beneficiary for all inpatient hospitalizations (for any cause) as reported in inpatient facility claims during the baseline period.
Outpatient facility use and spending	
Any outpatient visit	A binary indicator for whether a beneficiary had at least one claim for services provided by an outpatient facility for any cause during the baseline period.
Outpatient visit count	A count of the number of unique dates with an outpatient facility for any cause claim a beneficiary had during the baseline period.
Total outpatient spending	A continuous, non-negative variable representing the total amount paid by all parties for outpatient facility claims during the baseline period. This is calculated as the sum of the Medicare payment amount, the blood deductible liability amount, the non-Medicare payer amount, and the patient OOP amount.

BOEHRINGER INGELHEIM Group of Companies

NIS Protocol

BI Study Number 1199-0520

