Page 22 of 35

c42255024-02

Proprietary confidential information © 2023 Boehringer Ingelheim International GmbH or one or more of its affiliated companies

Variable	Description
OOP outpatient spending	A continuous, non-negative variable representing the total amount paid out-of-pocket by the beneficiary for services as reported in outpatient facility claims during the baseline period.
Home health use and spending	
Any home health	A binary indicator for whether a beneficiary had at least one claim for home health services during the baseline period.
Home health count	A count of the number of home health visits a beneficiary had during the baseline period, calculated by summing the total visit count on each claim across claims.
Total home health spending	A continuous, non-negative variable representing the total amount paid by all parties for home health claims during the baseline period. This is calculated as the sum of the Medicare payment amount, the blood deductible liability amount, the non-Medicare payer amount, and the patient OOP amount.
Part B spending	
Total Part B spending	A continuous, non-negative variable representing the total amount paid by all parties for Carrier and Durable Medical Equipment claims during the baseline period, calculated as the sum of the allowed amounts on each claim.
OOP Part B spending	A continuous, non-negative variable representing the total amount paid out-of-pocket by the beneficiary for Carrier and Durable Medical Equipment claims during the baseline period.
Total spending	
Total medical spending	A continuous non-negative variable representing the total amount paid by all parties for all medical services during the baseline period, including inpatient, outpatient, home health and Part B.
Total spending	A continuous non-negative variable representing the total amount paid by all parties for all medical and pharmacy claims during the baseline period and will be calculated as the sum of total pharmacy and total medical spending.
Other use	
Any ED visit	A binary indicator for whether a beneficiary had at least one emergency department visit during the baseline visit. Note that hospitals bill for emergency department visits on either the Inpatient or Outpatient facility claims, as described by

Variable	Description
	ResDAC here. Thus, emergency department visits will be identified in inpatient and outpatient facility claims via the presence of revenue center codes 0450-0459 and 0981.

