Potential confounding by observed covariates will be addressed in two ways, thus leading to "doubly robust" estimates. The first way is to calculate two sets of observation-level weights that balance covariates across exposure categories: inverse probability of treatment weights (IPTWs) and weights derived from a marginal mean weighting through stratification (MMWS) procedure (Hong, 2012; Linden, 2014). To generate the weights, a multinomial logit model of nintedanib adherence trajectory group category will be estimated as a function of the covariate roster. Predicted probabilities (i.e., propensity scores) for each category will be generated from the model results and used to calculate both the IPTW and MMWS

Proprietary confidential information © 2023 Boehringer Ingelheim International GmbH or one or more of its affiliated companies weights. Because multiple exposure categories are to be compared, the weights will provide estimates of the average treatment effect (ATE) (and not the average treatment effect on the treated [ATT]).

The second way confounding will be addressed is through regression adjustment; that is, observed covariates will be added to the GLM specification. Combining weighting with regression adjustment yields a double robustness property that attenuates bias in the case when either the treatment model (i.e., the multinomial logit model of exposure category) or the outcome model (i.e., the GLM of the health care resource use or spending outcome) is misspecified (Linden et al., 2016).

To facilitate interpretability, the regression model results will be transformed back to the scale of the outcome variable. Average marginal effects and their 95% confidence intervals (CIs) will be calculated using the delta method. Data preparation will be performed using SAS 9.4 (██████████) and data analysis will be conducted using Stata 17 (██████████).

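### The abstract promises baseline IPF-related cost and use as covariates, but the 9.3.3 roster has no IPF-coded measure, so two secondary outcomes go unadjusted for their own baseline

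*Combined protocol and SAP*

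**What the plan says.** The abstract, under Variables, names among the baseline covariates "clinical characteristics (e.g., comorbidity index, IPF-related health care costs and use), and all-cause health care costs and use". IPF-related and all-cause measures appear there as separate items.

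Section 9.3.3 is the operative list. It opens: "Study covariates are listed here and will be measured at the index date or during the 12 months prior". Its inpatient indicator is "at least one inpatient hospitalization for any cause during the baseline period", and total medical spending is "the total amount paid by all parties for all medical services during the baseline period".

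Section 9.7.1 says that the multinomial logit model behind both sets of weights "will be estimated as a function of the covariate roster", and that observed covariates are also added to the GLM.

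Section 9.3.2 makes all-cause medical cost primary. Two of its three secondary outcomes are IPF-related: "Total IPF-related medical costs", summed "for all medical services for an IPF-related reason (at least one IPF diagnosis code"), and IPF-related inpatient hospitalization.

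Section 9.9 lists as a limitation that claims omit determinants of the "outcomes that may be correlated with the adherence exposure, such as IPF disease severity".

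**The concern.** The protocol names a covariate in its summary and leaves it out of the list that the models use. Section 9.9 itself accepts the confounding path: severity drives use and cost and may be correlated with adherence. Prior IPF-coded admissions and spending are one claims-based window on that severity, and they are also the baseline values of two outcomes.

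A variable missing from 9.3.3 is missing from both the weights and the regression. Double robustness protects against misspecifying one of those two models. It does not protect against a confounder that is absent from both. At stake are some avoidable confounding and some lost precision for the IPF-related outcomes, and an adjustment set that the documents describe in two ways and that could therefore be settled after the data are seen.

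**Working it through.** **Text check.** Each outcome in 9.3.2 set against the roster in 9.3.3:

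| Outcome | Baseline counterpart in 9.3.3 |
|---|---|
| Primary: all-cause medical cost | Total medical spending |
| Secondary: all-cause hospitalization | Any inpatient stay, stay count, length of stay |
| Secondary: IPF-related medical cost | None |
| Secondary: IPF-related hospitalization | None |

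Going through the roster line by line, no covariate is defined by an IPF diagnosis code. Inpatient, outpatient, home health, Part B and total spending carry no IPF restriction. Several items do bear on respiratory severity or use: pulmonary hypertension, oxygen, hypoxia, ventilator use, pulmonary rehabilitation, HRCT, lung biopsy, any pulmonology visit, pulmonology visit count and pulmonology prescriber.

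**Can the missing variables be built?** Yes. Section 9.3.2 supplies the rule (at least one IPF diagnosis code), stated there for cost. Section 9.2.2 already requires a search of baseline inpatient and outpatient claims for IPF codes.

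**Size.** The plan gives no power calculation, outcome SD, event rate or severity imbalance, so there is no planned figure to reproduce. The 1,798 in 9.5 is what remained after sample selection.

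*Precision, from the documents.* Group sizes are 1,798 times the prevalences in 9.3.1 (43.1, 11.9, 10.4, 13.2 and 21.5%): about 775, 214, 187, 237 and 387. The prevalences sum to 100.1% through rounding. The unadjusted 95% CI half-width against the highly adherent group, in SD units and assuming equal SDs, is 1.96 × √(1/n1 + 1/n2):
- rapid decliners: 1.96 × √(1/775 + 1/387) = 0.122
- gradual decliners: 1.96 × √(1/775 + 1/187) = 0.160

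*Bias, on assumed inputs only.* Residual bias = b × d × (1 − R²), where b is the effect of severity on the outcome (SD per SD), d is the severity gap between groups (SD), and R² is the share of severity that the covariates capture. The bias removed is b × d × (gain in R²). I took b = 0.2 or 0.4, d = 0.1 or 0.3, and R² rising from 0.30 to 0.35, from 0.30 to 0.50, or from 0.10 to 0.40:
- smallest amount removed: 0.2 × 0.1 × 0.05 = 0.001 SD
- largest amount removed: 0.4 × 0.3 × 0.30 = 0.036 SD
- remaining after the fix: from 0.2 × 0.1 × (1 − 0.50) = 0.010 SD to 0.4 × 0.3 × (1 − 0.35) = 0.078 SD

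On these inputs the gain is real but modest, and more bias can remain than is removed.

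**The case against.** The strongest reply is that little would change. IPF-coded cost is part of the all-cause cost already in the roster, and IPF admissions are part of all-cause stays. An IPF-coded cost is not a clean severity measure either: any service carrying one code counts, so it also reflects diagnostic work-up and how early in the baseline year coding began, since 9.2.2 does not require a full year of coded IPF. Some listed items, such as pulmonary rehabilitation and pulmonology visits, can fairly be read as IPF-related use. Correcting the abstract would also remove the contradiction.

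Much of this stands. The omission is clear for IPF-coded cost and admissions and only partial for use in general, and the added information may be small. It does not remove the point. Two patients with equal total spending can differ in whether it arose from IPF admissions or from unrelated care, and none of the listed items measures IPF-coded admissions, days or cost. Overlap is not a new problem, since the roster already holds totals alongside their components. Correcting the abstract alone would leave two outcomes without their baseline values.

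A reader might infer from 9.9 that severity is simply written off. The documents do not support that: 9.9 is a fair limitation for directly measured severity, and the roster adjusts for several markers of it. Its gap is that it does not mention them.

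A reader might also attach a figure of 8 to 13% to the bias. If severe disease affected 40% of a declining group and 30% of the highly adherent group and multiplied cost by 2 or 3, the cost ratio would be inflated by (1 + 1 × 0.40)/(1 + 1 × 0.30) = 1.077 or (1 + 2 × 0.40)/(1 + 2 × 0.30) = 1.125. Every input there is assumed, and the result is crude confounding with no adjustment at all. It does not measure what is left after the existing roster is applied.

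**Conclusion.** The inconsistency between the abstract and 9.3.3 is established from the text. As written, IPF-related cost and IPF-related hospitalization are analysed without adjustment for their own baseline values. The argument about a missing baseline value does not extend to the primary outcome or to all-cause hospitalization, since both have counterparts in the roster.

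The gap is incremental. The documents do not allow its size to be calculated, and the range of 0.001 to 0.036 SD rests wholly on assumed inputs. Confounding by severity that claims do not measure would remain after the change. The point is worth acting on because the variables are promised, can be built from data already held, and are the natural baseline for two outcomes. It does not rest on a demonstrated large bias.

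**What to change.** Add three baseline variables to 9.3.3, and so to the propensity model and the outcome models:
- IPF-related medical cost
- any IPF-related inpatient stay
- IPF-related inpatient days

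Build them with the rule in 9.3.2 (at least one IPF diagnosis code), applied in the same way to the baseline and follow-up years, and state in advance the form in which cost enters the models.

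Because these variables are nested in the all-cause totals, check collinearity, and check that the weights remain stable, particularly in the smallest group (about 187 gradual decliners).

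Reword 9.9 to say that IPF severity is not measured directly and is captured only through claims proxies, that these are adjusted for, and that residual confounding remains likely. A short sensitivity analysis for unmeasured confounding, such as an E-value, would support that statement.

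The cost is minor programming for three derived variables and the two checks. No new data are needed.

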A prior study by this study team quantified nintedanib adherence trajectories using GBTMs and identified characteristics of patients associated with membership in each trajectory group. Individuals with idiopathic pulmonary fibrosis (IPF) who initiated nintedanib during 10/1/2014–12/31/2018 were identified in 100% Medicare claims and enrollment data. The sample consisted of community-dwelling older adults (≥ 66 years) with continuous coverage in Medicare Parts A, B and D for one year before (baseline) and after (follow-up) starting nintedanib. PDC was calculated for each of 12 consecutive 30-day months based on nintedanib claim fill dates and days’ supply. PDC was dichotomized, with PDC ≥ 0.8 considered adherent. A series of GBTMs of adherence was estimated to identify the best-fitting specification. Patients were then grouped based on their estimated adherence trajectories. Associations between baseline patient characteristics, including demographics, comorbidities, and health care use, and group membership probabilities were quantified as odds ratios using fractional multinomial logit modelling.

In this study, the best-fitting GBTM had five adherence trajectory groups: highly adherent (43.1%), medium adherent (11.9%), gradual decliners (10.4%), intermediate decliners (13.2%), and rapid decliners (21.5%) ([Figure 1](#)). The principal factors associated with higher odds of being in at least one of the lower-adherence groups were older age, female sex, race and ethnicity other than non-Hispanic white, and taking an additional medication during baseline.

Proprietary confidential information © 2023 Boehringer Ingelheim International GmbH or one or more of its affiliated companies

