9.2.2 Study population

- Inclusion criteria:
 - Newly initiated nintedanib during 10/01/2014 to 12/31/2018
 - Were at least 66 years old as of the date of their first nintedanib prescription claim (index date)
 - Qualified for Medicare based on age
 - Had at least 12 months of continuous enrollment in Medicare Parts A, B and D before (baseline period) and 12 months after the index date (follow-up period)
 - Had at least one inpatient or two outpatient claims (≥ 14 days apart) with a diagnosis code for IPF (ICD-10-CM: J84.112; ICD-9-CM: 516.31) during the baseline period
- Exclusion criteria:
 - Had any history of pirfenidone or nintedanib use during the baseline period
 - Had any history of lung transplant during the baseline, index date or follow-up periods
 - Had any claims for skilled nursing facility, long-term care facility or hospice during the baseline, index date or follow-up period
 - Had evidence (≥ 2 ICD-9-CM or ICD-10-CM diagnosis codes on different dates) during the baseline period of any of the following conditions: lung cancer, autoimmune, or connective tissue diseases (i.e., rheumatoid arthritis (RA), sarcoidosis, systemic lupus erythematosus (SLE), dermatopolymyositis, systemic sclerosis, Sjogren's, and mixed connective tissue disease (CTD)) during the baseline period (Appendix-1)
 - Had dual eligibility of Medicare and Medicaid.
 - Had history of using pirfenidone at the same time with nintedanib during follow-up

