9.3 VARIABLES**9.3.1 Exposures**

The exposure will be a categorical variable indicating which of the five nintedanib adherence trajectory groups a patient was most likely to belong, given their 12-month pattern of nintedanib claims as estimated from the GBTM. The groups (and their prevalence in the sample) are highly adherent (43.1%), medium adherent (11.9%), gradual decliners (10.4%), intermediate decliners (13.2%), and rapid decliners (21.5%).

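### No outcome has a stated accrual window, and the readable text implies that the primary cost accrues in the same 12 months that define the adherence group

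*Combined protocol and SAP*

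**What the plan says.** **Outcomes.** Section 9.3.2 states "The primary outcome will be total all-cause medical costs" and then lists IPF-related medical cost, all-cause hospitalization and IPF-related hospitalization as secondary. No outcome has an accrual period. Section 9.7.1 adds none.

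**Exposure.** The abstract describes "a five-category measure of adherence trajectory to nintedanib in the year following initiation". Section 7 says of the prior study that "PDC was calculated for each of 12 consecutive 30-day months". Section 9.3.1 assigns each patient to the most likely group "given their 12-month pattern of nintedanib claims as estimated from the GBTM".

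**Follow-up.** Section 9.1 plans two years for all patients. Section 9.2.2 requires continuous enrollment for 12 months "before (baseline period) and 12 months after the index date (follow-up period". Section 9.9 speaks of "at least 12 months of follow-up data after nintedanib initiation for primary outcomes (and 24 months for secondary outcomes". The abstract says that "the sample for analysis of the primary outcomes will consist of 1,798 Medicare beneficiaries with IPF", with a smaller secondary sample because of loss to follow-up.

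**Adjustment and aim.** Section 9.3.3 measures covariates at the index date or in the year before it. Section 9.7.1 combines weighting with regression adjustment and says that the weights target the ATE, not the ATT. Section 8 states both objectives as associations.

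**The concern.** If the primary cost accrues in months 1-12, exposure and outcome share one period and their order in time is unknown. A patient admitted in month 4 incurs inpatient cost and may stop or delay fills because of the admission. That patient then tends to be classed as a decliner and also to be expensive. A cost difference between decliners and the highly adherent group could arise in this way with no effect of adherence at all.

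Baseline weighting and regression adjustment do not help, because the path starts after index. Double robustness protects against a misspecified treatment or outcome model, not against a wrong time order.

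At stake is whether the main contrast can be read as non-adherence raising cost, or equally well as costly events ending adherence. Section 7 expects the findings to guide strategies for improving adherence, and that use needs the first reading.

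**Working it through.** **Step 1: the sections side by side.**

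| Section | What it implies about time |
|---|---|
| 4 (Variables), 7, 9.3.1 | Exposure: months 1-12 after first fill, 12 x 30 = 360 days |
| 9.3.2 | Outcomes: no window; primary and secondary differ by type of outcome |
| 9.1 | Two years of follow-up for all |
| 9.2.2 | Follow-up period is 12 months |
| 9.9 | 12 months for primary, 24 for secondary outcomes |
| 4 (Study size) | All 1,798 in the primary analysis, fewer in the secondary |

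Sections 9.9 and 4 separate primary from secondary by length of follow-up, but section 9.3.2 separates them by type. These statements need reconciling whatever was intended. The 1,798 patients were selected on 12 months of follow-up and all enter the primary analysis, so a months 1-12 cost window is the most natural reading. No readable sentence places primary cost after month 12.

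**Step 2: overlap.** For a 12-month cost window, 360/365 = 98.6% of outcome days are also exposure days. For 24 months counted from index, 360/730 = 49.3%. For months 13-24, about 0%. Section 9.9 does not say which of the last two its 24 months means.

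**Step 3: hand check that overlap alone can create a difference.** The inputs are assumptions, not figures from the documents: year-1 hospitalization risk 30%, background stopping 30%, no effect of adherence. A hospitalization also ends treatment with probability q.

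- P(decline | hospitalized) = 1 - 0.7 x (1 - q); P(decline | not hospitalized) = 0.30.
- q = 0: both equal 0.30, so the hospitalization ratio is 1.
- q = 0.10: decliners 0.111/(0.111 + 0.210) = 0.346; adherent 0.189/(0.189 + 0.490) = 0.278; ratio 1.24.
- q = 0.25: decliners 0.1425/(0.1425 + 0.210) = 0.404; adherent 0.1575/(0.1575 + 0.490) = 0.243; ratio 1.66.

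**Step 4: hypothetical cost figures.** A simulation with 400,000 patients per scenario and no drug effect. Assumed: 3% admission per month, inpatient care 50% of medical cost, permanent stopping, and background stopping tuned so that 55.0% continue (43.1% + 11.9%). Stoppers are ordered by time into rapid (21.5%), intermediate (13.2%) and gradual (the rest). The reference is all who continue. Three shapes of background stopping were tried: constant, proportional to 1/month, and five-fold in months 1-3.

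| Stays that end treatment | Year-1 excess cost, range over three decliner groups and three shapes |
|---|---|
| 0% | within about 1 point of zero |
| 2% | about 1-4% |
| 5% | about 3-10% |
| 10% | 7-18% |
| 20% | 15-37% |
| 30% | 24-54% |
| 40% | 35-72% |

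Repeat runs agree to about 2 points. Which decliner group shows the largest excess depends on the assumed stopping times, so no dose-response statement follows.

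**Step 5: months 13-24 under the same null.** The excess is about zero when severity does not persist. With strong assumed frailty, 3-16% (rapid) and 2-21% (gradual) remain, about 22-33% of the year-1 excess in the same scenarios. A later window reduces the bias but does not remove it.

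**Step 6: data span.** From 12/31/2018 to 12/31/2020 is 365 + 366 = 731 days, more than 24 x 30 = 720. The data span cuts off no patient's second year.

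**The case against.** **The overlap is never stated.** Section 9.9 gives required follow-up, not an outcome window, and Figure 2, which is not shown, may mark the windows. This stands, and it limits confidence in the overlap. It does not supply the windows that the text of section 9.3.2 lacks.

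**A later window may already be intended.** Section 9.1 builds in two years, section 9.9 assigns 24 months to secondary outcomes, and the abstract expects loss to follow-up. This stands too. A reader might infer that no second-year analysis is planned, and the documents do not support that. The request may amount to defining one.

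**The aim is association.** Concurrent measurement is a legitimate descriptive design, and section 7 cites work on both coincident and subsequent use. A reader might take ATE as a causal claim, but section 9.7.1 uses it to distinguish the weighting target from the ATT. The term can stay. What remains is that a concurrent association cannot by itself support the use foreseen in section 7.

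**Section 9.9 partly covers this.** Its list is not presented as complete, and it names unmeasured severity and selection. But severity there is a confounding issue. The problem here would remain even if baseline severity were measured perfectly.

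**The simulated sizes follow from their inputs.** This stands. Every scenario lets stays trigger stopping and none includes an opposing path, so the runs are not evidence of sign. Selection may also shrink the figures, because section 9.2.2 excludes patients who "Had any claims for skilled nursing facility, long-term care facility or hospice during the baseline, index date or follow-up period". If that removed 60% of stays that end treatment and 20% of the others (assumed), the excess over the 10-40% rows would be 3-24% for rapid and 4-36% for gradual decliners.

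**Conclusion.** The concern holds as a gap in definition with a real consequence. With high confidence, the readable text defines no accrual window for any outcome and conflicts on follow-up. With moderate confidence, the primary cost window coincides with the exposure window. If it does, costly admissions can by themselves produce the primary contrast, the planned adjustment cannot remove this, and section 9.9 does not say so.

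The size cannot be derived from the documents. The figures of 1-4% (2% of stays ending treatment) up to tens of percent (20-40%) are hypothetical and rest on assumed rates of admission, stopping and inpatient share. A reader might infer that the study's result will be inflated by a known amount, or that the direction is proven. The documents support neither. This should be fixed, and the improvement is cheap.

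**What to change.** 1. In section 9.3.2, state the start and end of accrual for each outcome. Reconcile the abstract and sections 9.1, 9.2.2, 9.3.2 and 9.9 on follow-up and on what separates primary from secondary outcomes.
2. Keep the months 1-12 exposure. Add, or if already intended define, an analysis of all-cause medical cost and hospitalization in months 13-24 with stated handling of death and disenrollment. One option is to censor at disenrollment with inverse-probability-of-censoring weights, and to end accrual at death while reporting deaths and cost per month alive by group.
3. Describe the months 1-12 result as a concurrent association, and rest no statement about the effect of adherence on it alone. ATE may remain as the name of the weighting target.
4. Add reverse causation from overlapping windows to section 9.9, and note that months 13-24 remain open to unmeasured severity and survivor selection.

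**Cost.** Wording changes, plus at most one analysis on data already planned. The second-year sample will be smaller and selected. Assumed losses of 10/20/30% leave about 1,618/1,438/1,259 of 1,798 patients, and standard errors grow by 1/sqrt(1 - loss), that is by about 5/12/20%.
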